10.3. SECONDARY OUTCOME MEASURE: TIME TO 50% AND 75% GRAFT HEALING	22
10.4. SECONDARY OUTCOME MEASURE: OPERATIVE TIME	22
10.5. SECONDARY OUTCOME MEASURE: NAC SENSITIVITY	23
10.6. SECONDARY OUTCOME MEASURE: NIPPLE PROJECTION	23
10.7. SECONDARY OUTCOME MEASURE: NIPPLE DIAMETER	23
10.8. SECONDARY OUTCOME MEASURE: PATIENT SATISFACTION	24
10.9. SECONDARY OUTCOME MEASURE: NAC VASCULARIZATION	24
11. REGULATORY CONSIDERATIONS	25
11.1. INSTITUTIONAL REVIEW OF PROTOCOL.....	25
11.2. DATA AND SAFETY MONITORING PLAN.....	25
11.3. DATA MANAGEMENT PLAN	25
12. STATISTICAL CONSIDERATIONS	26
12.1 STATISTICAL DESIGN	26
12.2. INTERIM ANALYSES.....	27
12.3. DESCRIPTIVE STATISTICS AND EXPLORATORY DATA ANALYSIS	27
12.4. PRIMARY ANALYSIS.....	27
12.5. SECONDARY ANALYSIS.....	27
12.6. SAMPLE SIZE.....	28
12.7. CRITERIA FOR FUTURE STUDIES	28
13. REFERENCES.....	29
APPENDIX A: PARTICIPANT ELIGIBILITY CHECKLIST.....	31
APPENDIX B: NIPPLE RECONSTRUCTION SATISFACTION SURVEYS	33

PROTOCOL SYNOPSIS

[figure not shown]
TITLE	A Single Arm, Single Center Pilot Study Evaluating the Safety and Healing Time of the NACgraft™ for Nipple-Areolar Complex Reconstruction
STUDY PHASE	Feasibility
INDICATION	Nipple-Areola Complex (NAC) Reconstruction
INVESTIGATIONAL PRODUCT OR PROCEDURE	NACgraft™ - a decellularized skin allograft of the human nipple-areolar complex
PRIMARY OBJECTIVE(S)	To evaluate safety and healing time after NAC reconstruction with the BioAesthetics' NACgraft™.
SECONDARY OBJECTIVE(S)	To evaluate operative time, NAC vascularization, dimensions, sensation, and patient satisfaction up to 12 months after reconstruction surgery with the BioAesthetics' NACgraft™.
TREATMENT SUMMARY	
This single arm pilot study is designed to obtain preliminary safety, healing, patient satisfaction and other data in adult female subjects undergoing uni- or bilateral nipple-areola complex reconstruction with the BioAesthetics' NACgraft™.
 
The study consists of a screening period (up to 3 weeks before engraftment) to determine study eligibility and prepare the NACgraft(s)™, a treatment period during which time uni- or bilateral engraftment surgery is performed, and a follow-up period during which time safety, healing time, vascularization, nipple dimensions and sensitivity, and patient satisfaction are assessed.
 
The total duration of the study is approximately 13 months for each subject.
 
Up to 20 female subjects will be screened in order to perform NAC engraftment on 15 subjects. Primary, secondary and exploratory endpoints will be assessed up to 12 months after engraftment.
 
On the day of surgery, NACgrafts™ will be engrafted according to standard reconstructive technique. Using sterile technique, the recipient site on the breast mound will be de-epithelialized sharply and meticulous hemostasis obtained with electrocautery. The NACgraft™ will then be sutured into place. In women undergoing bilateral NAC reconstruction, this process will be repeated for the contralateral breast. A sterile dressing will be applied and patients will be discharged home according to institutional guidelines; written

	
instructions will be provided for the care of the NACgraft(s)™ and dressings. The dressing will include antimicrobial ointment, followed by a non-adherent, occlusive dressing (e.g. Adaptic, Xeroform) secured in place using a foam dressing cut into a donut (e.g., Allevyn) to prevent compression of the graft.
 
Patients will be return to the outpatient clinic regularly until the graft(s) are fully healed: on or about postoperative Days 7, 14, 28, and 42. They will return on days 90, 180, and 360 for measurement of long-term endpoints including nipple dimensions, sensitivity, and for satisfaction survey completion.

SAMPLE SIZE	N=15 patients
STATISTICAL CONSIDERATIONS	Time to complete healing for each NAC will be defined as the first weekly visit at which the graft has been deemed to be >99% epithelialized. Max, Mean, Median, and 95% Confidence Interval of these data will be presented, as will percent (%) healed over time for each graft. No formal statistical testing will be performed for any other endpoint; summary statistics will be presented at each time point.

SCHEMA

Inclusion Criteria:

- Patient age 18-65
- Patient desires NAC grafting \geq 3 months after autologous breast reconstruction
- Patient agrees to sleep on back until grafts healed (6 weeks)
- Patient agrees to abstain from aspirin, smoking, alcohol (>2 drinks per day), or excessive caffeine (>300mg per day) until grafts healed (6 weeks)
- Patient agrees to not undergo NAC tattooing until completing study (12 months)
- Patient is able to understand and willing to sign informed consent.

LIST OF ABBREVIATIONS AND DEFINITION OF TERMS

AE	Adverse Event
BD-NRC	Biodesign® Nipple Reconstruction Cylinder
BMSC	Bone Marrow-Derived Mesenchymal Stem Cell
BMI	Body mass index
CGTP	Current Good Tissue Practices
CRF	Case Report Form
CTCAE	Common Terminology Criteria for Adverse Events
Dcl-NHP-NAC	Decellularized Non-Human Primate Nipple-Areolar Complex
DSMC	Data Safety Monitoring Committee
ECOG	Eastern Cooperative Oncology Group
ECM	Extracellular Matrix
FDA	Food and Drug Administration
GCP	Good Clinical Practice
HCT/P	Human Cells, Tissues, and Cellular and Tissue-Based Products
HIPAA	Health Insurance Portability and Accountability Act
HIV	Human Immunodeficiency Virus
IDE	Investigational Device Exemption
IRB	Institutional Review Board
NAC	Nipple-areolar complex
NACgraft™	Decellularized human nipple-areolar complex graft
NHP	Non-Human Primate
N-NAC	Native Nipple-Areolar Complex
PD	Protocol Director
SAE	Serious Adverse Events
SRC	Scientific Review Committee
SWM	Semmes Weinstein Monofilament
VAS	Visual Analog Scale

1. OBJECTIVES

1.1. Primary Objective

To evaluate safety and healing time after nipple-areola complex reconstruction with the BioAesthetics' NACgraft™.

1.2. Secondary Objectives

To evaluate operative time, NAC vascularity, dimensions (projection, sensitivity), sensitivity, and patient satisfaction up to 12 months after nipple-areola complex reconstruction surgery with the BioAesthetics' NACgraft™.

2. BACKGROUND

2.1. Study Disease

There are over 3.5 million breast cancer survivors in the US, many of whom have undergone reconstructive surgery.¹ Close to one-third of early stage and two-thirds of late-stage breast cancer patients opt for mastectomies.^{1,2} Patients without a NAC continue to experience psychological distress even after the breast mound has been reconstructed.³ NAC reconstruction is of key psychological importance for these patients, decreasing feelings of distress and increasing body image and self-esteem.^{4,5} Women with NAC reconstruction have significantly higher sexual well-being, aesthetic and general satisfaction, and quality of life scores, as compared to women without NAC reconstruction.^{6,7} However, there is no standard, viable method to reliably reconstruct a permanent and natural NAC. Current NAC reconstruction options are limited to rubber prostheses, 3D tattoos, and surgical techniques to create NAC-like structures from a patient's own skin tissue or acellular dermal allografts.⁸⁻¹⁰ These approaches produce NACs that either lack physical depth or fail to maintain a protrusion for more than a few months.^{11,12} According to breast reconstructive surgeons, current methods of nipple reconstruction are the limiting factor for a complete breast reconstruction.

2.2. Study Device

The BioAesthetics NACgraft™ is a decellularized NAC derived from deceased human donors. Proprietary washing/rinsing steps provide a removal of immunologic elements (including cells and nucleic acids). The NACgraft™ is then packaged in a tube containing sterile PBS for individual attachment to a de-epithelialized portion of the human breast after breast reconstruction and is protected with dressings until re-vascularization, re-epithelialization and dermal/neural elements repopulate the device, leaving a living human NAC substitute. By preserving the ECM of the native human NAC, including its non-immunogenic signaling molecules and structural format, the BioAesthetics NACgraft™ serves as a scaffold that allows vascular, neural, dermal and epithelial infiltration until the time of complete healing. The BioAesthetics NACgraft™ has been studied extensively in *in vitro* and in preclinical models including mice and non-human primates to demonstrate their safety and therapeutic potential, as detailed in Section 2.5.^{21,22}

BioAesthetics' NACgraft™ fits within the Food and Drug Administration (FDA)'s HCT/P (Human Cells, Tissues, and Cellular and Tissue-Based Products (21 CFR Part 1271)) regulatory pathway (see Appendix A1 of Investigator's Brochure). To advance to clinical use, the product is manufactured in accordance with Current Good Tissue Practices (CGTP) and must submit a registration with the FDA 90 days prior to marketing. The NACgraft™ will be registered with the FDA prior to study initiation. Therefore, no Investigational Device Exemption (IDE) is required for this feasibility study.

2.3. Rationale

Over 200,000 mastectomies are performed annually in the US for the prevention or treatment of breast cancer.¹ These surgeries involve the partial or complete removal of the breast tissue, including the NAC. Additionally, more than 3.5 million breast cancer survivors are living in the US, many of whom have had mastectomies.¹ Close to one-third of early stage and two-thirds of late stage breast cancer patients opt for mastectomy as a treatment.^{1,2} Following mastectomy, over 70% of women elect to undergo reconstruction.¹³ NAC reconstruction can have a significant impact on a woman's psychological well-being.¹⁴⁻¹⁶ Women are more comfortable undergoing a mastectomy if the nipple can be spared during the procedure, or if nipple reconstruction is possible when nipple-sparing is not an option.¹⁷ Research has shown that the NAC may play a more significant role in determining psychological well-being than the reconstructed breast mound. NAC reconstruction has been shown to correlate with self-esteem and improved body image. Furthermore, NAC reconstruction provides a sense of closure to their cancer experience.^{4,5} Close to 80% of women who underwent NAC reconstruction would describe NAC reconstruction as being important and would encourage other women to undergo NAC reconstruction.⁶ Women with NAC reconstruction are described feeling more confident in social settings, more emotionally capable, emotionally healthy, self-confident, feminine, attractive, and "normal".⁶ Women with NAC reconstruction have higher sexual well-being, general and aesthetic satisfaction, and quality of life scores compared to women without NAC reconstruction.^{6,7}

Despite the widespread popularity and health benefits of post-mastectomy NAC reconstruction, current options for reconstruction are often inadequate. Options for NAC reconstruction include three-dimensional (3D) tattooing, adhesive prosthetics, acellular collagen matrix derived from porcine intestinal submucosa, or surgical techniques to create NAC-like structures from skin tissue such as local flaps or nipple-sharing grafts, or acellular dermal matrix sheets.⁸⁻¹⁰ Unfortunately, these approaches either lack physical depth or fail to maintain a 3D structure for more than a few months.^{11,12} Patient outcomes for surgical NAC reconstruction are dependent on surgical skill and time, and patients often end up requiring additional costly revisions when their reconstruction NAC(s) lose projection. Furthermore, nipple-sharing grafts are not feasible for all patients and only available for women who have had a unilateral mastectomy and have a nipple of adequate size.¹⁸ Use of decellularized porcine small intestinal submucosa, such as Cook Medical's Biodesign® Nipple Reconstruction Cylinder (BD-NRC) has had mixed results, retaining only an average of 40% nipple projection at 12 months post reconstruction.¹² Thus, there remains a great need for an easy-to-apply, permanent, and aesthetically pleasing method for NAC reconstruction.

These clinical challenges inspired the BioAesthetics group to develop the NACgraft™, which serves as a scaffold for NAC regeneration that can be engrafted onto the exterior of the body on a de-epithelialized wound bed (onlay engraftment) in the anatomical location of the NAC. The NACgraft™ onlay graft differs from previous acellular allografts, which are intended for subcutaneous placement. This graft undergoes a patent-pending decellularization process which has been rigorously developed, characterized, and published in peer-reviewed journals.^{19,20}

2.4. Study Design

This **single arm** pilot study is designed to obtain preliminary safety and performance data in adult female subjects following **treatment** with the BioAesthetics' NACgraft™. NACgrafts will be surgically engrafted onto 15 patients, via uni- or bilateral onlay engraftment. Given the nature of the treatment, this is an **open** (no masking) trial. **No randomization** will occur. The primary outcome being evaluated is **safety/efficacy** of the treatment approach. The overall study design is as follows:

- Potential patients will be screened to determine study eligibility up to 3 weeks before the engraftment.
- On the day of surgery, NACgrafts will be engrafted according to standard reconstructive technique. Using sterile technique, the recipient site on the breast mound will be de-epithelialized sharply and meticulous hemostasis obtained with electrocautery. The NACgraft™ will then be sutured into the wound bed with dissolving suture. In women undergoing bilateral NAC reconstruction, this process will be repeated for the contralateral breast. A sterile dressing will be applied and patients will be discharged home according to institutional guidelines; written instructions will be provided for the care of the NACgraft(s) and dressings. The dressing will include antimicrobial ointment, followed by a non-adherent, occlusive dressing (e.g. Adaptic, Xeroform) secured in place using a foam dressing cut into a donut (e.g., Allevyn) to prevent compression of the graft.
- Safety, healing time, sensation, vascularization, patient satisfaction, and nipple characteristics will be assessed over a 12-month period. Patients will return to the outpatient clinic on postoperative Days 7, 14, 28, and 42. Visits thereafter will take place on days 90, 180, and 360 post-engraftment.

2.5. Correlative Studies Background

The BioAesthetics NACgraft™ has been studied extensively in *in vitro* and in preclinical models to demonstrate their safety and therapeutic potential, as detailed below.^{21,22}

In a recent study,²¹ NAC tissue was harvested from rhesus macaques according to institutional guidelines and decellularized through a modified protocol.^{23,24} Briefly, NAC grafts are incubated with a series of agents alternating with water including Triton X-100, sodium deoxycholate, sodium chloride, antibiotic/antimycotic agents, and DNase I, then stored in antibiotic/antimycotic solution until use. This process removes cellular components while preserving the extracellular matrix (ECM) structure. Decellularized NACs were subjected to histological and quantitative analyses, including culture with bone marrow-derived mesenchymal stem cells (BMSCs) *in vitro*. They were found to be completely devoid of cells while retaining ECM integrity and a high degree of bioactivity. Specifically, collagen and glycosaminoglycan content were not significantly altered by decellularization, whereas elastin content was significantly decreased. The graft promoted BMSC proliferation and viability *in vitro*.

In a follow up study, nonhuman primate (NHP)-derived NAC tissue was decellularized and their ECM components analyzed by both proteomic and histological analyses.²² Decellularized NHP NAC grafts again showed the removal of intact cells and a greatly diminished intracellular protein profile, as compared with intact NHP NAC tissue. Decellularized NAC grafts were then tested in a murine model. N=15 mice received subcutaneous implantation of a decellularized-NHP-

NAC (dcl-NHP-NAC group 1 and 2). Additional groups included native NAC (N-NAC), commercial control (Strattice, catalog No. 1016002; LifeCell Corporation, Branchburg, NJ), or surgery only (sham). Two dcl-NHP-NAC groups were included to reflect different decellularization batches. Tissue was harvested at days 2, 14, 21. Histology revealed greater neovascularization in dcl-NHP-NAC grafts as compared to the commercial control, with no observed biocompatibility issues. The grafts were then tested in an NHP model. Briefly, 18 dcl-NHP-NACs and two native host nipples were onlay grafted onto partial thickness wounds along the dorsal midline of rhesus macaques. Grafts were harvested at weeks 1, 3, and 6 for histological analysis. Results demonstrated successful neovascularization of the grafts that reached a steady state by 3 weeks post-engraftment. Furthermore, grafts showed complete re-epithelialization by 3 weeks, which remained unchanged through the end of the study.

This approach has now been replicated using human-derived NAC grafts implanted in an NHP model (manuscript in preparation). Results showed graft re-epithelialization, vascularization, and the presence of nerves within graft tissue by the 6-week timepoint, with preserved nipple projection. In summary, the above preclinical trials confirm the safety and clinical potential for this device to improve patient care.

2.6 Nipple Morphology and Pigmentation Considerations

When a NAC is recovered from a deceased donor, the areola diameter, nipple diameter, and nipple projection/height are measured. These characteristics and pertinent demographic information (age, race, BMI, etc.) will be tracked with each NAC as part of inventory. For consistency in the manufacturing process, the diameters of the areolas are uniformly sized to 2 cm, but the diameters (usually < 2 cm) and projections of the nipples themselves are not altered. We will categorize the NAC grafts as small, medium, and large on the basis of both nipple diameter and projection. In speaking with patients, it is clear that each has a unique preference for nipple size. When the physician places an order, the size preference will be matched from the inventory.

With respect to pigmentation, the process of decellularization generally removes all pigment (melanin) from the graft such that it appears as a pale white color just like Alloderm® or other acellular dermis products. In individuals with very darkly pigmented NACs, we sometimes see that a layer of melanin remains on the surface of the NAC graft after decellularization. In our studies of NAC graft engraftments on non-human primates whose skin lacks melanin, we saw that after healing occurred (6 weeks) the color of regenerated NAC was the same as the surrounding skin tissue, but with a pink hue due to blood vessel infiltration. On a microscopic level, what we saw is that cells infiltrated the graft and lined up along the basement membrane between the epidermis and dermis of the NAC graft and regenerated a new epidermis underneath the existing decellularized epidermis, sloughing off the decellularized epidermis. So, from these observations, we expect that regardless if melanin (only contained in the epidermis) remains on the surface of the graft or not after decellularization, it will be sloughed off during the healing process and the graft will take on the color of the patient's surrounding skin. Therefore, we expect that NAC grafts do not need to be matched for race. Since non-human primates do not have melanin, we could not ascertain from those studies whether the NAC grafts promote higher concentrations of melanocytes/melanin than normal skin and, therefore, result in a darker

pigmented NAC as compared to surrounding skin. If a patient is not satisfied with the color of their new NAC, tattooing can be performed after healing is complete.

3. PARTICIPANT SELECTION AND ENROLLMENT PROCEDURES

Refer to the Participant Eligibility Checklist in Appendix A.

3.1. Inclusion Criteria

- 3.1.1. Women between 18 and 65 years old. No race-ethnic restrictions.
- 3.1.2. Patient has undergone uni- or bi-lateral autologous breast reconstruction a minimum of 3 months prior to enrolling in the study.
- 3.1.3. Patient agrees to sleep on her back until the graft(s) have healed (approximately 6 weeks).
- 3.1.4. Patient agrees to abstain from taking aspirin, drinking alcohol (>2 drinks per day), or consuming excessive amounts of caffeine (>300mg per day) until the graft(s) have healed (approximately 6 weeks).
- 3.1.5. Patient agrees to not undergo NAC tattooing until completing the study (approximately 12 months after engraftment).
- 3.1.6. Patient is able to understand and willing to sign an informed consent form.
- 3.1.7. Eastern Cooperative Oncology Group (ECOG) or Karnofsky Performance Status restrictions: N/A
- 3.1.8. Life expectancy restrictions: N/A
- 3.1.9. Requirements for organ and marrow function: N/A

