4.2. Criteria for Removal from Study

Reasons for patient withdrawal from the study include the following:

- Patient withdraws consent.
- Patient has disease progression (e.g., breast cancer recurrence on the side(s) of NAC reconstruction), requiring additional treatment such as surgery or chemotherapy.
- Unacceptable adverse events, such as infection, hematoma, or allergic reaction requiring removal of the NACgraft.
- The patient fails to comply with the study guidelines or postoperative care instructions (such as non-adherence with tobacco)
- Any other medical condition which would place the patient at unnecessary risk if they were to continue in the study, determined on a case-by-case basis.

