5.2. Intervention Description

This is a single-arm interventional study. The study group will undergo NAC reconstruction in the office or operating room depending on any concurrent procedures. Following antiseptics and injection of local anesthesia, an area of skin on the reconstructed breast mound is de-epithelialized with a scalpel. After obtaining hemostasis with bovie electrocautery, the graft is sewn in place using an absorbable suture. A soft dressing is then placed over the graft (antibiotic ointment, non-adherent occlusive dressing, foam/sponge dressing cut into a donut). The dressing is taken down on postoperative day 7 at the patient's first follow up appointment. Dressings are continued until epithelialization is complete over the entire graft (this is anticipated to occur over 4-6 weeks). The Foam dressings will be used for 6 weeks to prevent graft compression.

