11.2. Data and Safety Monitoring Plan

The Stanford Cancer Institute Data and Safety Monitoring Committee (DSMC) will be the monitoring entity for this study. The DSMC will audit study-related activities to determine whether the study has been conducted in accordance with the protocol, local standard operating procedures, FDA regulations, and Good Clinical Practice (GCP). This may include review of the following types of documents participating in the study: regulatory binders, case report forms, eligibility checklists, and source documents. In addition, the DSMC will regularly review serious adverse events and protocol deviations associated with the research to ensure the protection of human subjects. Results of the DSMC audit will be communicated to the IRB and the appropriate regulatory authorities at the time of continuing review, or in an expedited fashion, as needed.

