12.4.1. Analysis Population

All study participants will be included in the analysis population. Intention-to-treat analysis will be performed and statistics for sub-groups containing no missing data or non-adherence will be included.

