APPENDIX A: Participant Eligibility Checklist

Protocol Title:	A Single Arm, Single Center Pilot Study Evaluating the Safety and Healing Time of the NACgraft™ for Nipple-Areolar Complex Reconstruction
Protocol Number:	
Principal Investigator:	[name]

II. Subject Information:

Subject Name/ID:
Gender:  Male  Female

III. Study Information:

SRC Approved IRB Approved Contract signed

IV. Inclusion/Exclusion Criteria

Inclusion Criteria (From IRB approved protocol)	Yes	No	Supporting Documentation*
1. Patient is between 18 and 65 years of age, inclusive.			
2. Patient has undergone uni- or bi-lateral autologous breast reconstruction a minimum of 3 months prior to enrolling in the study.			
3. Patient agrees to not undergo NAC tattooing until completing the study (approximately 12 months after engraftment).			_____ Provider initials/Date
4. Patient agrees to sleep on her back until the graft(s) have healed (approximately 6 weeks).			_____ Provider initials/Date
5. Patient agrees to abstain from aspirin, smoking, alcohol (>2 drinks per day), or excessive caffeine (>300mg per day) until grafts healed (6 weeks).			_____ Provider initials/Date
6. Patient is able to understand and willing to sign an informed consent form.			_____ Provider initials/Date
Exclusion Criteria (From IRB approved protocol)			
1. Patient is currently smoking or using tobacco or nicotine products (i.e. patch, gum, or nasal spray) or has used such products in the past 12 months.			
2. Patient has a history of delayed wound healing.			

3. Patient has a Vitamin C deficiency.			
4. Patient has diabetes (Type I or Type II).			
5. Patient has any uncontrolled comorbidity.			
6. Patient has a body mass index <18.5 or >40 kg/m ² .			
7. Patient is currently receiving radiation or chemotherapy or received radiation to the breast wall.			

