APPENDIX B: Nipple Reconstruction Satisfaction Surveys

Nipple Reconstruction Satisfaction Survey: Pre-operative

You have undergone breast reconstruction after mastectomy and are about to undergo nipple reconstruction with the BioAesthetics NACgraft. The following questions are designed to determine how you are feeling at this time. Please answer each question. Thank you for your feedback.

	Male	Female				
What is your sex?						
	< 18	19 – 35	36 – 50	51 – 65	> 66	
What is your present age?						
	< 3 months	3 – 6 months	6 – 9 months	9 – 12 months	> 12 months	N/A
How long ago was your left breast reconstruction (if applicable)?						
How long ago was your right breast reconstruction (if applicable)?						
				Yes	No	
I agree to sleep on my back for 6 weeks after nipple reconstruction.						
I agree to abstain from aspirin, smoking, excessive alcohol (no more than 2 drinks per day), and excessive caffeine (no more than 300mg per day, or 3 cups of coffee) for 6 weeks after nipple reconstruction.						
I agree to not undergo nipple tattooing for 12 months after nipple reconstruction.						
	Strongly Disagree	Disagree	Neither Agree nor Disagree	Agree	Strongly Agree	N/A
I am satisfied with the shape of my new left breast.						
I am satisfied with the shape of my new right breast.						
I would undergo breast reconstruction again.						
				Yes	No	N/A
My left breast was eligible for a nipple-sparing mastectomy, but I chose to have my nipple removed.						
My right breast was eligible for a nipple-sparing mastectomy, but I chose to have my nipple removed.						

Nipple Reconstruction Satisfaction Survey: Pre-operative

	No Sensation	Low	Normal	High	N/A
What level of pleasant sensation do you have in your left breast?					
What level of pleasant sensation do you have in your right breast?					
What level of unpleasant sensation do you have in your left breast?					
What level of unpleasant sensation do you have in your right breast?					
I had a nipple-sparing mastectomy on my left breast. The sensation in my left nipple is					
I had a nipple-sparing mastectomy on my right breast. The sensation in my right nipple is					
Answer the following items as compared to before your mastectomy.	Much Worse	Worse	About the same	Better	Much Better
My sense of body image is					
My sense of self-esteem is					
My sense of well-being is					
My sex life is					

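### Withdrawing women for non-compliance (4.2) conflicts with the promised all-participant analysis and, because precautions run until healing, loses slow healers more often

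*Combined protocol and SAP*

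**What the plan says.** Four parts of the combined protocol and SAP bear on this.

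- **Withdrawal.** Section 4.2 lists reasons for withdrawal from the study. One is "The patient fails to comply with the study guidelines or postoperative care instructions", with tobacco as the example. It gives no period and does not say whether healing and safety are still recorded afterwards.
- **Analysis population.** Sections 12.4.1 and 12.5.1 put every participant in the analysis, call it intention-to-treat, and add that "statistics for sub-groups containing no missing data or non-adherence will be included". Neither defines non-adherence.
- **Length of the precautions.** Section 3.1.3 reads "Patient agrees to sleep on her back until the graft(s) have healed (approximately 6 weeks", and 3.1.4 uses the same end point. The schema has "Patient agrees to sleep on back until grafts healed (6 weeks", and Appendix A item 5 has "excessive caffeine (>300mg per day) until grafts healed (6 weeks". The pre-operative survey in Appendix B has a flat period: "I agree to sleep on my back for 6 weeks after nipple reconstruction". Section 5.2 also sets a flat period for the dressing: "The Foam dressings will be used for 6 weeks to prevent graft compression".
- **Recording of lapses.** The study calendar records current medications, which could show aspirin use. It has no line for sleep position, smoking, alcohol or caffeine. Section 11.2 says "the DSMC will regularly review serious adverse events and protocol deviations associated with the research", so deviation records are one stated route.

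**The concern.** The graft is placed once. A woman who later sleeps on her side or drinks too much coffee still has the graft, and its healing and complications can still be seen. Withdrawing her discards primary outcomes that an intention-to-treat analysis needs, and no section says how her missing healing time would enter the summary.

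The loss need not be even. If a lapse can count at any time until healing, a woman who takes longer to heal is at risk of withdrawal or exclusion for longer. The women who remain are then faster healers on average, even if lapses have no effect on healing. The primary healing summary and the supplementary one could both look somewhat too favourable to the graft. Sections 12.1 and 12.6.2 give preliminary estimates for a larger study as one purpose of this pilot.

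**Working it through.** The plan states no figure on this point, so there is none to reproduce. The check asks how far the mean moves under assumed values.

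**Inputs from the documents.** There are 15 women. Scheduled healing visits are on Days 7, 14, 28 and 42, and the next visit is Day 90 (90/7 = 12.86 weeks). Section 5.2 expects epithelialization over 4 to 6 weeks.

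**Assumed inputs.** The weekly chance of a first lapse is h = 1, 2, 5 or 10%, the same for all women and unrelated to healing. Every lapse in the window leads to withdrawal or exclusion. Each woman has one graft.

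**Formula.** A woman healing at week T and at risk for W weeks is retained with probability k = (1 - h)^W. The mean among retained women is sum(p·T·k) / sum(p·k), where p is the share healing at T.

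**Unequal loss.** With W = T and h = 5%, the chance of being lost is:
- healed at week 4: 1 - 0.95^4 = 18.5%
- healed at week 6: 1 - 0.95^6 = 26.5%
- healed at Day 90: 1 - 0.95^12.86 = 48.3%

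**Worked case.** Take half healing at week 4 and half at week 6 (true mean 5.00), with h = 10%. Then k = 0.6561 and 0.5314, and the retained mean is (4 × 0.6561 + 6 × 0.5314) / (0.6561 + 0.5314) = 4.90, a shift of -0.10 weeks.

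**Shift in mean weeks, for h = 1/2/5/10%**

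| Assumed healing | True mean | Window to healing | Window to healing or week 6, whichever is first | Flat 6 weeks |
|---|---|---|---|---|
| 50% week 4, 50% week 6 | 5.00 | -0.01/-0.02/-0.05/-0.10 | same | 0 |
| 40% week 4, 40% week 6, 20% Day 90 | 6.57 | -0.10/-0.21/-0.49/-0.90 | -0.02/-0.04/-0.11/-0.22 | 0 |

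If the late 20% are instead recorded at week 8 (true mean 5.60), the to-healing shift is -0.02/-0.05/-0.11/-0.23.

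**Against sampling error.** In the 50/50 case the SD is 1.00, so the standard error at n = 15 is 1.00/√15 = 0.26. In the Day 90 case it is 3.27/√15 = 0.84.

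**Outcomes lost.** In the 50/50 case the expected number of the 15 women whose healing time is lost is 15 × [1 - ((1-h)^4 + (1-h)^6)/2] = 0.7/1.4/3.4/6.1.

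**Withdrawal differs from exclusion.** A flat 6-week count applied to the sub-group drops women at the same rate whatever their healing time, so the shift is zero. Withdrawal loses a healing time only when the lapse comes before healing. Under a flat 6-week instruction, withdrawal therefore still follows the capped column. A common window alone does not repair 4.2; continued follow-up does.

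**A mismatch reverses the sign.** Suppose women healed at week 4 are released then, half of them stop the precautions, and lapses are counted to Day 42 for everyone. In the 40/40/20% Day 90 case the sub-group mean then shifts by +0.63/+0.61/+0.56/+0.46 weeks. The instruction and the counting window must match.

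**The case against.** The strongest reply is that the plan never makes the 3.1.3 window its definition of non-adherence. Sections 3.1.3 and 3.1.4 are agreements made at entry, and no section links them to 12.4.1 or 12.5.1. Appendix B and the foam dressing already point to a flat 6 weeks, and every version carries the same nominal period. This stands: the documents show an undefined term, and the tilt follows only under one reading of it.

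The size is also open to challenge. The larger shifts need women who heal after Day 42, and 10.1.4 allows extra early visits, so such women need not wait until Day 90 to be recorded. The -0.90 figure also needs a 10% weekly lapse rate, which no document supports. This stands as well.

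A reader might go further and infer any of the following. The documents support none of them.

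- *The plan's healing estimate is biased by up to about a week.* That figure comes wholly from the assumed tail and lapse rate.
- *Any lapse means withdrawal.* Section 4.2 lists reasons and does not say how strictly they are applied.
- *The go-ahead decision rests on the sub-group.* Section 12.7 does not mention it, the study is descriptive, and all participants are the main population.
- *A Day 0 to 42 count is simply correct.* It is a trade-off. It counts lapses after healing, which cannot affect healing time, and ignores later lapses in women still unhealed.

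None of this answers the gap in 4.2. Withdrawal after a one-time graft, with no statement on follow-up, does not fit an intention-to-treat promise under any reading of the window.

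**Conclusion.** This is a minor point that holds in a limited form. Section 4.2 as written can remove women whose primary healing and safety outcomes 12.4.1 promises to analyse. If precautions run to healing, as 3.1.3 and 3.1.4 say, those lost are more often slow healers. The direction follows from the length of exposure for any lapse rate above zero. The size is unknown: about -0.01 to -0.10 weeks if all grafts heal by week 6, at assumed weekly lapse rates of 1 to 10%, and more only with an assumed late tail. In the 50/50 case even the largest shift is below the standard error of 0.26 weeks. The loss of outcomes in a study of 15 may matter as much as the tilt.

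The all-participant analysis is unaffected provided women who lapse are still followed. A common window removes only the exposure-length effect in the sub-group. If slow healers lapse more for other reasons, or lapses delay healing, some selection remains there.

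**What to change.** 1. **Section 4.2.** State that non-compliance does not end follow-up. Engrafted women who lapse stay in the all-participant analysis and, if they agree, keep the scheduled healing and safety visits. This is the change that matters most.
2. **Sections 12.4.1 and 12.5.1.** Label the no-non-adherence statistics as supplementary to the all-participant results.
3. **Sections 3.1.3 and 3.1.4, the schema and Appendix A.** Adopt the flat 6 weeks of Appendix B, and use the same 6 weeks for counting lapses in 12.4.1 and 12.5.1, whatever the date of healing. Change the instruction and the count together, because changing only the count can reverse the shift.

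The cost is wording and an IRB modification, with no new patients and no new visit types. Women who would have been withdrawn attend a few more of the existing visits. A woman healed at week 4 keeps the precautions two weeks longer, although foam dressings already run 6 weeks. The reported healing figure may be slightly less favourable.
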